5.0 Inclusion and Exclusion Criteria/ Study Population

- **Inclusion Criteria:** Infants, 6-18 months old with hemiplegia/motor asymmetry who qualify for CIMT, Gross Motor Function Classification System (GMFCS) level I-IV (a validated classification system with 5-levels that describe the gross motor function of children with cerebral palsy based on their self-initiated movements, in sitting, walking and mobility).⁴⁸ Prior CIMT therapy will be allowed if the infant has not had CIMT in the preceding 3 months.
- **Exclusion Criteria:** GMFCS level V,⁴⁸ severe motor impairment/quadriplegic involvement; uncorrected blindness or deafness, cardiomyopathy. CIMT therapy within the prior 3 months.

6.0 Number of Subjects

We will enroll up to 10 infants aiming to collect data on at least 5 completed courses of CIMT+taVNS.

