We expect infant motor skills to improve with 40h CIMT+ taVNS, from before to the end of treatment, with maintenance of motor skill gains at 3months after completion of CIMT (n=5 complete the course of CIMT+taVNS).

This is the first application combining neuromodulation and the proven intervention of CIMT in infants.

We need to show feasibility and generate pilot data in a small number of patients prior to submission of an NIH proposal on pairing taVNS and CIMT for rehabilitation of infants with hemiplegia after perinatal brain injury (see [name] Letter of Support). This application expands our success with our previous NM4R pilot grant, which culminated in a taVNS infant system designated as an FDA Breakthrough Device. We will use this device in a completely unexplored area of neuromodulation, that of taVNS paired with intensive CIMT rehabilitation in young infants. Our goal with this combination neuromodulatory strategy is to decrease the severity of clinical deficits in infants, to improve day-to-day living, ameliorate life-long motor deficits, and help both the child and their families.

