3.0 Intervention to be studied

Proposed Trial of CIMT Paired with taVNS

We will treat up to 10 infants referred for CIMT with one-sided motor weakness to receive active taVNS paired with 40 hours of CIMT. We will perform infant motor assessments before and after the treatment is completed to answer the following questions:

- 1) Is taVNS feasible and safe of in infants 6-18months of age undergoing CIMT therapy?
- 2) Does infant motor ability increase with low-dosage 40h CIMT + active taVNS as measured by: 1) upper extremity motor abilities, 2) gross motor skills, and 3) individual treatment goals.

Experimental set-up: For this proposal we will modify our BabyStrong system, which uses the FDA cleared Soterix taVNS unit, Neolead® electrode in front of the tragus and custom ear electrode for infant sized ears, wired trigger control of stimulation with a trigger button or direct input in the Soterix taVNS unit. We will substitute a portable, therapist-triggered taVNS system with hand held trigger button as seen in **Figure 6**. The therapist will activate a hand-held button for 2min-on/30 sec-off control of stimulation during a CIMT session.

We have an established, collaborative, innovative multidisciplinary team to execute these proposed studies. In addition to MUSC's infant taVNS trial, Drs. [name] and [name] have been collaborating for 10 years on infant developmental assessments and other therapeutic studies. [name] has been an innovator in CIMT in young infants and has investigated modified CIMT approaches in the U.S. and abroad.^{37,45-47} These studies provided evidence of how to modify signature pediatric CIMT approaches, while adhering to the essential elements of the therapy, to assure high levels of treatment efficacy. Pertinent to this trial, she also published the first case report on successful implementation of CIMT in infants under one year of age.³⁷

Working with development, perhaps activating critical motor synapses, taVNS paired with CIMT could deliver groundbreaking innovation in the increasing problem of unilateral motor weakness in infants with perinatally acquired brain injury.

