4.0 Study Endpoints

Aim 1: Primary CIMT feasibility outcomes: Ability of therapist to operate taVNS easily and successfully by earning a meeting or exceeding score (3 or 4) on random videotaped therapy sessions, as scored by CIMT fidelity treatment.

Aim 1: Primary taVNS safety and feasibility outcomes: Ability of infant to tolerate wired ear electrode and for electrode to remain securely in place with good contact with minor manipulation during sessions; <5% of sessions with sustained discomfort requiring decreasing current.

Aim 2: Primary Efficacy Outcome: We will use the Quality of Upper Extremity Skills Test (QUEST) subtests for grasp and dissociated movement as our primary outcome. The QUEST is a reliable, valid, quantitative outcome measure with excellent psychometric properties, and is recommended by NINDS/NICHD for the evaluation of movement patterns and hand function in children with cerebral palsy.⁴⁹ The subtests for grasp and dissociated movement have been used in published infant CIMT trials,⁸ and provide detailed information on hand function and quality of movement between the right and left sides of the body.

Aim 2: Secondary Efficacy Outcomes: We will use three other assessments for fine and gross motor function and meeting individual treatment goals: Developmental Assessment of Young Children (DAYC), the Gross Motor Function Measure-66 (GMFM-66) and the Goal Attainment Scale (GAS).

- The DAYC is a standardized assessment of early developmental skills from birth to 5 years of age⁵⁰ and is recommended for early detection of CP.⁵¹ We will use the DAYC Physical Development domain to assess developmentally appropriate fine and gross motor skills. [Mean (SD)=100±15 for each domain.]
- We will use the GMFM-66 as a comprehensive evaluation of foundational gross motor skills to assess how much of a task the infant can do rather than the quality of motor performance.^{48,52,53} Specific sections tested include Dimensions (A) Lying & rolling, (B) Sitting, (C) Crawling & kneeling, (D) Standing.^{52,53}
- The GAS is an individualized outcome measure that is standardized in order to calculate the extent to which a patient or group of patients' therapy goals are met.^{54,55} We will set individual goals for each infant and use the GAS scale to analyze differences between before and after CIMT+taVNS.

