The parents of infants who present for CIMT are highly motivated, and willing to commit to the time and effort commitment for CIMT. Most of the study procedures occur during the active treatment period. Therefore, we anticipate >95% retention to completion of the immediate outcome measures. For the 3 months follow-up assessment, we will call every month to discuss infant progress with the mother/caregiver. All of these infants will also have regular developmental follow-up in MUSC's or other high-risk clinic, and we will collect this data with parent consent, though it is not part of the primary or secondary outcomes for the phase I trial.

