10.0 Study Design / Methods

Overall Study Design: This study will determine the feasibility, and safety of therapist-directed taVNS paired with CIMT therapy in n=10, 6-18month old infants with hemiplegia after perinatally acquired brain injury. We will measure the effect of active taVNS paired with 40 hours of CIMT on infant motor skills before and after treatment over a month, and follow up the motor skills over 3 months. All infants will receive active taVNS treatment. CIMT treatment is a non-research procedure, and motor and developmental testing are non-research procedures. taVNS is a research procedure. CIMT sessions will be videotaped, to measure the fidelity of CIMT delivery while the therapist is delivering taVNS to determine feasibility.

The alternative treatment is the usual and customary occupational therapy services. If parents wish, they may pursue CIMT therapy with local therapists, but there are very few qualified therapists in the area.

We will monitor for and mitigate following risks are present with this study: Risk of skin irritation, risk of discomfort, risk of slightly decreased heart rate, and risk of loss of confidentiality.

Risk of skin irritation: we will monitor the skin on the inner aspect of the left ear before and after each session, and will switch to the right ear if redness is present, and decrease the stimulation if redness persists.

Risk of discomfort: We will protect against the risk of discomfort by close monitoring. We will use the mother's perception of infant discomfort and infant signs of discomfort to determine the perceptual threshold, and then treat at 0.1mA less than this level of perception. If any infant seems to be in discomfort during the CIMT taVNS session, we will decrease the microcurrent by 0.1mA, as in our feeding taVNS trial in infants. We will use facial expression change, fidgety movements and infant vocalization as signs of behavioral discomfort, to indicate need for decreasing the microcurrent during the taVNS session.

We will not continuously monitor heart rate during the taVNS session, as our extensive HR data in infants show no bradycardia and no decrease in HR beyond 60 seconds after starting stimulation.

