14.0 Withdrawal of Subjects

Parents may withdraw their infants at any time. Reasons may include excessive demands of time for CIMT or family pressures. Infants may be withdrawn without parental consent, if taVNS is poorly tolerated. If either occur, parents will be referred for clinical CIMT, or if this is not possible within the parent's home structure, other occupational and physical therapy as appropriate. We will continue to collect follow-up data on motor skills even with early termination, if infants continue with USC OT department.

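### No Aim 1 feasibility outcome counts the infants who start taVNS with CIMT but do not finish the course

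*Combined protocol and SAP*

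**What the plan says.** **Enrolment.** Section 6.0 states: "We will enroll up to 10 infants aiming to collect data on at least 5 completed courses of CIMT+taVNS". Section 3.0 agrees on the ceiling: "We will treat up to 10 infants referred for CIMT with one-sided motor weakness to receive active taVNS paired with 40 hours of CIMT". The expectation for Aim 2 in section 1.0 rests on completers ("n=5 complete the course of CIMT+taVNS"). Section 10.0 gives the number without the qualifier: "This study will determine the feasibility, and safety of therapist-directed taVNS paired with CIMT therapy in n=10, 6-18month old infants".

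**Feasibility and safety outcomes.** Section 4.0 lists these for Aim 1:
- therapist fidelity, judged by "earning a meeting or exceeding score (3 or 4) on random videotaped therapy sessions";
- electrode tolerance and contact, introduced as "Primary taVNS safety and feasibility outcomes: Ability of infant to tolerate wired ear electrode";
- sustained discomfort that requires a lower current, in under 5% of sessions.

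**Retention and withdrawal.** Section 8.0 says "we anticipate >95% retention to completion of the immediate outcome measures". Section 13.0 lists retention rates among the items for IRB progress reports. Section 14.0 says of withdrawal by parents: "Reasons may include excessive demands of time for CIMT or family pressures". It also allows withdrawal for poor tolerance of taVNS. It does not say how withdrawn infants count towards feasibility.

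**The concern.** Sections 1.0 and 2.0 argue that intensive CIMT is hard to fit into family life. The course here is 20 two-hour sessions in four consecutive weeks, and section 8.0 notes that some families travel far. Non-completion is thus a failure that the plan itself foresees. Yet the feasibility outcomes describe sessions, or tolerance in general terms, and not the share of infants who begin and finish.

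The pilot is meant to show feasibility before a larger grant proposal. Without completion among all starters, a favourable feasibility statement could describe mainly the infants who stayed. The next trial would then lack a figure that it needs for planning.

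**Working it through.** **Inputs.** At most 10 enrolled and at least 5 completed courses (section 6.0); 2 hours × 5 sessions a week × 4 weeks (section 3.0, Table 1); retention above 95% anticipated (section 8.0); discomfort in under 5% of sessions (section 4.0). The plan gives no derivation of 10 or 5, so there is no calculation to reproduce. The dose does reproduce: 5 × 4 = 20 sessions, and 2 × 20 = 40 hours.

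**1. What the enrolment range permits.** Starters needed for five completers = 5 / completion proportion.
- At 95%: 5/0.95 = 5.3, so 6 infants. The chance that at least 5 of 6 complete is 0.95⁶ + 6 × 0.95⁵ × 0.05 = 0.967.
- At 50%: 5/0.50 = 10 infants, which is the cap.

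The target can therefore be met with half of the starters completing. If true completion were 50%, at least 5 of 10 would complete with probability 0.623.

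**2. What a completion proportion would show.** Exact (Clopper-Pearson) 95% intervals, ten starters:

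| Completed | Proportion | 95% CI |
|---|---|---|
| 5/10 | 50% | 18.7% to 81.3% |
| 8/10 | 80% | 44.4% to 97.5% |
| 9/10 | 90% | 55.5% to 99.7% |
| 10/10 | 100% | 69.2% to 100% |

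With ten or fewer starters, one dropout already gives 90% or less, so the anticipated figure above 95% means no dropout at all.

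**3. Whether a stated level would be workable.** The level of 8/10 is assumed for illustration only. It would be reached with probability 0.055 if true completion were 50% and 0.988 if it were 95%. At least 5 of 10 would be reached with probability 0.623 and above 0.999.

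**4. Whether the session-based discomfort limit closes the gap.** Assume that completers have no session with sustained discomfort.
- Five complete (5 × 20 = 100 sessions) and five stop after one session, each with discomfort: 5/105 = 4.8%. The limit is met; per infant the figure is 5/10 = 50%.
- Five complete and five stop after two sessions, one of them with discomfort: 5/110 = 4.5%. The limit is met.
- As above, but both sessions with discomfort: 10/110 = 9.1%. The limit is not met.
- Seven complete (140 sessions) and three stop after one session with discomfort: 3/143 = 2.1%. The limit is met; per infant the figure is 3/10 = 30%.

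The 4.8% example leaves no slack, since one more such session gives 6/105 = 5.7%. The last example leaves ample room. A withdrawal for time or family reasons adds nothing to the numerator of the discomfort rule and has no place in the other outcomes.

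**The case against.** The strongest reply is that the feasibility question is narrow: can a therapist deliver taVNS without losing CIMT fidelity, and do infants tolerate it? Section 10.0 treats CIMT as a non-research procedure, so a family that leaves because of CIMT's time demands says little about adding taVNS. This stands in part, and it is why reasons for stopping should be tabulated with the proportion. It does not remove the need for the proportion, because the proposal under test is the combined 40-hour course.

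It can also be said that non-completion would not be hidden. Retention goes to the IRB, parents and therapist complete weekly questionnaires, and section 14.0 continues follow-up after early termination for infants who stay with the OT department. Families are described as highly motivated, and the dose is below the 60 to 120 hours of other programmes. All of this is correct, but none of it is an Aim 1 outcome.

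Four stronger readings are tempting, and the documents do not support them.
- *Half of the infants could fail and every goal still be met.* Infants withdrawn for poor tolerance bear directly on the electrode outcome, vague as it is. Five such withdrawals could not plainly be called success. The gap is complete only for time and family withdrawals.
- *Dropouts will be replaced until five infants complete.* Section 6.0 gives a ceiling and a floor, with no replacement rule and no stop at five.
- *Enrolment could end when results look good, inflating the error rate.* Section 12.0 plans no interim test and states no significance level, so no such error rate can be attributed to the plan.
- *The sample size is contradictory.* The statements fit one plan, up to 10 enrolled and at least 5 completing. Only section 10.0 omits the qualifier.

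**Conclusion.** The point holds as a gap in the Aim 1 outcomes. No feasibility criterion uses infants who started as its denominator, time and family withdrawals enter none of them, and early stopping for discomfort can be diluted by the sessions of completers.

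The size is bounded by what the plan permits: completion as low as 5/10 at the cap, against an expectation above 95%. The 4.8% figure assumes that each withdrawn infant has one session and that completers have no discomfort. It shows what the rule allows and is not a forecast.

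The gap does not undermine the trial. It limits what a feasibility conclusion can say, and it should be closed before the first infant is treated.

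**What to change.** 1. Add to section 4.0, as an Aim 1 feasibility outcome, the number of infants completing the 20-session course divided by all infants who received a first taVNS session. Give reasons for stopping and an exact 95% CI.
2. Before the first infant, state the completion proportion that the investigators would regard as feasible. The level is theirs to choose; the intervals above show how little ten infants can settle.
3. Report sustained discomfort per infant as well as per session, with every starter counted.
4. Align the n=10 of section 10.0 with the ceiling in sections 3.0 and 6.0, and state that enrolment will not stop on the basis of accumulating results. Enrolment should also not be set to end at the fifth completion. The number of starters would then be random, the fixed-sample exact interval would no longer fit, and at 95% completion the trial would end at about 5/0.95 = 5.3 infants.

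The cost is protocol wording. Daily therapy logs (section 3.0, Table 1) and retention reports (section 13.0) already hold the data. The downside is that the feasibility result may look less favourable.

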7.0 Setting

CIMT treatment sessions will occur in College of Health Professions (CHP) pediatric therapy lab located in the CHP B Building at [name].

8.0 Recruitment Methods

We have IRB approval for two pilot studies (#67997, #103800) in preterm and term stroke/HIE infants with taVNS paired with feeding using similar taVNS study procedures as proposed in this application. The taVNS system has a non-significant risk device designation from MUSC's IRB in these two pilot trials.

[name] will screen for infants in the nursery with known brain injury that will likely lead to hemiparesis or weakness, such as perinatal arterial stroke, HIE, severe IVH, PVL or cerebellar infarct, regardless of sex or race. The clinical team will inform the parents of the potential to participate in the study. [name] will then explain the study to the parents and give them contact information if they are interested, to initiate screening and consent procedures when their infant reaches 6-8months of age. Infants are also referred directly to [name] and [name] specifically for CIMT from a wide region of the southeast. Because some parents travel great distances to get these services, we may obtain referrals from other care providers out of our region. We will perform phone screening and obtain Econsent prior to patient arrival for patients whose parents cannot meet in person prior to the first treatment session, to be able to get services fully prepared for the visit. We will use the approved REDcap system to obtain consent. [name] or other approved study personnel will go over the entire consent document on the phone with the parent to ensure comprehension and to confirm identity. Parent will be given a copy of the completed, signed consent form in person or by email or fax.

Volunteers of all ethnicities and racial categories will be accepted into this study protocol. No preference will be given based on race, gender or ethnicity. Young infants who had perinatal complications leading to perinatally acquired brain injury may be considered vulnerable populations and are the target of this proposal.

The parents of infants who present for CIMT are highly motivated, and willing to commit to the time and effort commitment for CIMT. Most of the study procedures occur during the active treatment period. Therefore, we anticipate >95% retention to completion of the immediate outcome measures. For the 3 months follow-up assessment, we will call every month to discuss infant progress with the mother/caregiver. All of these infants will also have regular developmental follow-up in MUSC's or other high-risk clinic, and we will collect this data with parent consent, though it is not part of the primary or secondary outcomes for the phase I trial.

9.0 Consent Process

Drs. [name], [name], or [name] (PI and Co-Investigators) will explain the study to these parents by phone or conference call and obtain written informed consent when they and their infants present to the Occupational therapy department for CIMT. Based on our 87% consent rate in the pilot taVNS-feeding study, and the ready parental acceptance of taVNS, we anticipate no significant parental concerns that would impact enrollment. We will not have a Spanish language consent.

We will perform phone screening and obtain eConsent prior to patient arrival for patients whose parents cannot meet in person prior to the first treatment session, to be able to get services fully prepared for the visit. We will use the approved REDcap system to obtain consent. [name] or other approved study personnel will go over the entire consent document on the phone with the parent to ensure comprehension and to confirm identity. Parent will be given a copy of the completed, signed consent form in person or by email or fax.

10.0 Study Design / Methods

Overall Study Design: This study will determine the feasibility, and safety of therapist-directed taVNS paired with CIMT therapy in n=10, 6-18month old infants with hemiplegia after perinatally acquired brain injury. We will measure the effect of active taVNS paired with 40 hours of CIMT on infant motor skills before and after treatment over a month, and follow up the motor skills over 3 months. All infants will receive active taVNS treatment. CIMT treatment is a non-research procedure, and motor and developmental testing are non-research procedures. taVNS is a research procedure. CIMT sessions will be videotaped, to measure the fidelity of CIMT delivery while the therapist is delivering taVNS to determine feasibility.

The alternative treatment is the usual and customary occupational therapy services. If parents wish, they may pursue CIMT therapy with local therapists, but there are very few qualified therapists in the area.

We will monitor for and mitigate following risks are present with this study: Risk of skin irritation, risk of discomfort, risk of slightly decreased heart rate, and risk of loss of confidentiality.

Risk of skin irritation: we will monitor the skin on the inner aspect of the left ear before and after each session, and will switch to the right ear if redness is present, and decrease the stimulation if redness persists.

Risk of discomfort: We will protect against the risk of discomfort by close monitoring. We will use the mother's perception of infant discomfort and infant signs of discomfort to determine the perceptual threshold, and then treat at 0.1mA less than this level of perception. If any infant seems to be in discomfort during the CIMT taVNS session, we will decrease the microcurrent by 0.1mA, as in our feeding taVNS trial in infants. We will use facial expression change, fidgety movements and infant vocalization as signs of behavioral discomfort, to indicate need for decreasing the microcurrent during the taVNS session.

We will not continuously monitor heart rate during the taVNS session, as our extensive HR data in infants show no bradycardia and no decrease in HR beyond 60 seconds after starting stimulation.

Risk of loss of confidentiality: We will check the infant's medical records to gather the following information: gestational age at birth, ventilator support, head ultrasound and MRI results, bottle feeding, infection, neonatal condition during labor and delivery, infant's treatments and conditions, and developmental progress.

We will assign study numbers to each participant, keep CRF and consent forms in locked offices. Database files with names and contact information will be password protected and stored on the MUSC Pediatric server. All other data files related to this study will be identified by participant number only, without link to standard identifiers. We will publish the aggregate data only.

